## 11 ANALYTICAL METHODS

### 11.1 Data Analysis

Appropriate analytical methods will be used to interpret the study results. Techniques may include:

- Descriptive statistics and graphical plots (i.e., box and whisker plots) to assess the central tendency and variability of the raw data
- Distribution diagnostics and outlier test to determine degree of nonlinearity and other systematic error. All missing data will be assumed to be missing-at-random, unless trends are detected.
- Any statistical analysis will be performed using JMP Statistical Software, Version 15.0 (SAS Institute Inc., Cary, NC.)

### 11.2 Lost to Follow-up

Data on subjects who are lost to follow-up or who withdraw from the study will be maintained and analyzed up to the point at which they discontinued. The reason for withdrawal will be recorded if known. Subjects who discontinue participation, for whatever reason, will remain in the study and be subject to follow-up in the same manner as those who complete the study except as noted above. The only confirmed lost to follow-up subject will be the subject who dies or refuses to continue to participate in the study and withdraws.

### 11.3 Sample Size Estimate

This is an Investigator Initiated Study; there is no formal sample size calculation. A minimum of thirty ( $\geq 30$ ) IPVs on at least twenty ( $\geq 20$ ) and a maximum of thirty ( $\leq 30$ ) subjects will be enrolled.

- 1) Along with the available Real-World Evidence data, the number of IPVs proposed is satisfactory compared with number of IPVs used in other early studies performed for “Substantial Equivalence” 510k pathways requiring human data in the field of thermal ablation for venous reflux.
- 2) Based on Real World Evidence and MAUDE database review, the number of AEs and MDRs, respectively, is very low. If a study is designed to evaluate what is already observed in RWE, it would drive sample sizes for statistical justification to be extremely high, which is overly burdensome to demonstrate “substantial equivalence”.
- 3) Based on review of the technical features of the predicate device vs. subject device, the set-point temperature and thermal ablation size are “substantially equivalent”. This means the thermal spread is the same providing reasonable level of assurance of safety and effectiveness. The proposed sample size for this study is large enough to understand any differences in performance between subject and predicate devices.
- 4) Post-hoc review of the study results will be performed on any AEs and/or occlusion data to determine if results provide an acceptable level of substantial equivalence.

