## Section 3 – INVESTIGATION PLAN

### CLINICAL PROTOCOL SUMMARY

Title:	Investigator Initiated Safety Study Using the Venclose Vestico (commercial name TBD) Radiofrequency (RF) Ablation System for the Treatment of Incompetent Perforator Veins (IPVs)
Synopsis:	
An Investigator Initiated study conducted to evaluate the safety of the Venclose digiRF Generator with Vestico Catheter System (“Vestico”) treating incompetent perforator veins (IPVs). The study will be conducted in compliance with IDE requirements under local IRB approval(s). Study data will be summarized and submitted to FDA in a premarket notification once all subjects have completed 30-day follow-up.
 
Venclose’s venous ablation technology is already cleared by FDA for use in treating chronic venous insufficiency, especially treating saphenous and branching veins, and has been in clinical practice since 2017 with extremely low adverse events. The study’s working hypothesis is that using the Venclose Vestico Catheter System will safely treat incompetent perforator veins (IPVs) without resulting in any adverse outcomes related to use of the device.
 
A physician with extensive clinical background and experience in treating vascular and venous diseases and a medical license to practice in the United States will use the Vestico device to treat a minimum of 30 IPVs on at least twenty (<math>\geq 20</math>) and a maximum of thirty (<math>\leq 30</math>) subjects.

Description of Intervention:	Following informed consent, the physician operator will gain access to the IPV in the leg using ultrasound guidance. The Vestico device will be inserted into the vein lumen also with ultrasound imaging guidance and the target treatment position confirmed. After providing local anesthesia to the vein and surrounding tissues, the Vestico device will be activated to deliver the thermal ablation energy to the vessel. Once the treatment cycle has been completed the device will be withdrawn and closure confirmed with duplex ultrasound. A bandage and compression hose will be applied. The patient will then immediately ambulate.
Number of Sites:	Single Site
Objectives:	

1) The study’s working hypothesis is that using the Venclose Vestico Catheter System for treating incompetent perforator veins (IPVs) will not result in significant adverse outcomes related to use of the device.

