Incompetent perforator vein treatment using the Venclose Vestico Catheter System uses the same mechanism of action (MOA) as the Medtronic RFS procedure cleared by FDA (K number) for IPVs as well as the same MOA as the Venclose EVSRF procedure previously cleared by the FDA (K number) for thermally ablating Saphenous reflux. The only difference between the RFS and the Vestico/EVSRF technology is the mode of thermal energy delivery which is bipolar energy delivered directly to the patient tissues for RFS vs. patient isolated resistive heating for the Vestico/EVSRF technology. Thermal energy (i.e., heat energy; time-at-temperature) is what effects successful collagen denaturation and vessel occlusion. Both bipolar and resistive technologies accomplish the same result (i.e., both impart heat energy to occlude the vessel). In the case of the Vestico system, the resistive heating technology is inherently safer since the patient (i.e., patient's tissues) is not used as part of the electrical circuit which is the case for the FDA cleared RFS device currently in use today. Additionally, resistive heating technologies like the Venclose EVSRF and Medtronic ClosureFAST technologies have proven to be the standard of care for much larger diameter vessels than required for treating perforator veins. Consequently, based on the understanding of the thermal effects on collagen, and on the typical size of the target vein anatomy, these resistive heating technologies are well-suited for successful treatment of incompetent perforators.

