## **2.2 Study Outline**

The study's working hypothesis is that using the Venclose Vestico Catheter System for treating incompetent perforator veins (IPVs) will not result in significant adverse outcomes related to use of the device.

There will be an informed consent/consultation visit and an intervention visit. A pre-operative Duplex Ultrasound imaging will be obtained prior to or during the consultation visit. The Vestico device will be used to treat IPVs during the intervention visit. Safety assessments and pre- and post-treatment Duplex Ultrasound imaging will be obtained measuring reflux during the primary intervention. Safety assessments and post-operative Duplex Ultrasound images will be obtained within 3 days after the intervention. All subjects will be followed up at 15 days and 30-days post-operatively for a safety assessment and Duplex Ultrasound. No further study intervention, study visits or study-specific data collection will follow the 30-day follow-up. The subject population will be patients in need of treatment for Chronic venous insufficiency (CVI) and disease due to IPVs.

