### **2.2.4 Device Description**

The Venclose Vestico System uses resistive radiofrequency ablation (via energy delivered to heat the wall of an incompetent vein) with temperature-controlled RF energy, and an already widely accepted procedure to cause irreversible luminal occlusion. This is followed by fibrosis and ultimately resorption of the vein.

Venclose Vestico System consists of two (2) main components:

- 1) Vestico catheter with integrated cable connector which treats the vein in 0.5 cm segments (Figure 1) and
- 2) Venclose digiRF generator (model VC-RFG-1) which delivers radiofrequency (RF) energy to the Vestico catheter (digiRF generator already cleared under, K160754) (Figure 2).

Figure 1: Vestico Catheter

Figure 2: Venclose digiRF Generator

The Vestico catheter is a slight modification to the sponsor's already cleared EVSRF catheter (K160754) for the treatment of superficial veins. The primary components of the catheter, as illustrated in Figure 3, include the shaft, handle and integrated connector cable. The catheter shaft is 6 French (6F = 2.0 mm in diameter) in profile, with an insertable length of 40 cm and a 0.5 cm heating coil, which is energized by the digiRF generator. The shaft's lumen allows passage of a guidewire 0.025" or smaller in diameter to help steer the catheter into position within the vasculature, as needed.

The technology and design used in the Vestico catheter is identical to the EVSRF catheter and developed based on special considerations for human factors and usability engineering with features included to provide easy handling for the operator. The parent technology of EVSRF catheter used in Vestico with human factors testing has been reviewed and cleared by the FDA. Briefly, the catheter handle includes a manual start/stop button, the circuitry for communication with the generator, and a luer connector for flushing of the guidewire lumen prior to catheter insertion into the vein (Figure 3). The button on catheter gives full control of the device operation to the user, such as to activate or terminate treatments, or to pause and re-start as necessary.

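### Section 11.3 item 3 claims the sample can reveal any performance difference from the predicate, a property that a single-arm study of 20 to 30 subjects with no stated benchmark does not have

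*Combined protocol and SAP*

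**What the plan says.** Section 11.3 (Sample Size Estimate) states openly that "there is no formal sample size calculation" and sets a minimum of 30 IPVs in 20 to 30 subjects. Four numbered items of rationale follow.

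- Item 1 appeals to the size of other early studies, without figures.
- Item 2 says AEs and MDRs are very low in existing data, and that if a study were designed to evaluate what is already seen there, "it would drive sample sizes for statistical justification to be extremely high".
- Item 3 compares set-point temperature and ablation size, infers safety and effectiveness from their similarity, and concludes: "The proposed sample size for this study is large enough to understand any differences in performance between subject and predicate devices".
- Item 4 plans a post-hoc review of AEs and/or occlusion data "to determine if results provide an acceptable level of substantial equivalence".

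On the design, section 2.2 says: "The Vestico device will be used to treat IPVs during the intervention visit". No other treatment is given. The word predicate occurs only in item 3, without a device name. Two cleared devices appear elsewhere. Section 2.1 says that Vestico treatment "uses the same mechanism of action (MOA) as the Medtronic RFS procedure cleared by FDA (K number) for IPVs", and section 2.2.4 describes the Vestico catheter as a modification of the sponsor's "already cleared EVSRF catheter (K160754) for the treatment of superficial veins". Neither is labelled the predicate, and no clinical result is given for either. Section 11.1 lists descriptive techniques that may be used and no comparison.

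**The concern.** A claim that a sample is large enough to reveal differences needs a comparator, a reference rate, a size of difference and a way to judge it. None of these is stated. The sentences that lead up to the claim concern technical similarity, which cannot show how many clinical observations are enough.

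The sentence matters because of where the results go: "Study data will be summarized and submitted to FDA in a premarket notification". Item 4 then uses AEs and occlusion to judge substantial equivalence without a criterion. Read together, items 3 and 4 make it easier for a finding of no observed difference to pass as evidence of no difference. In a sample of this size, no observed difference is a likely result even when a moderate difference exists.

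**Working it through.** **What can be reproduced.** Nothing. The document gives no significance level, power, rate, difference or margin. The check is therefore what 20 to 30 subjects and 30 IPVs can show. The sample sizes come from section 11.3. The benchmarks, test levels and correlations below are my assumptions.

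**Adverse events, per subject.** With zero events of a given type, the exact two-sided 95% upper limit is 1 − 0.025^(1/n).

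- n = 20: 1 − 0.025^(1/20) = 16.8%
- n = 30: 1 − 0.025^(1/30) = 11.6%

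The chance of seeing no event at true rate p is (1 − p)^n.

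| True rate | n = 20 | n = 30 |
|---|---|---|
| 1% | 82% | 74% |
| 2% | 67% | 55% |
| 5% | 36% | 21% |

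Zero is the likelier result when p is below 1 − 0.5^(1/n), which is 3.4% at n = 20 and 2.3% at n = 30. At a true rate of 5%, at least one event is the likelier result.

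**Occlusion, per vein, 30 independent IPVs.** Take a benchmark p0 fixed in advance. Declare a shortfall if the number occluded X is at most c, where c is the largest value with P(X ≤ c | 30, p0) no greater than the test level. Power is P(X ≤ c | 30, p0 − 0.10) or P(X ≤ c | 30, p0 − 0.20).

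| Assumed p0 | One-sided 5%: c | 10 points | 20 points | One-sided 2.5%: c | 10 points | 20 points |
|---|---|---|---|---|---|---|
| 95% | 25 | 48% | 90% | 25 | 48% | 90% |
| 90% | 23 | 39% | 84% | 22 | 24% | 72% |
| 80% | 19 | 27% | 71% | 18 | 16% | 57% |
| 70% | 16 | 29% | 71% | 15 | 18% | 57% |

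The ranges are 27 to 48% and 71 to 90% at one-sided 5%, and 16 to 48% and 57 to 90% at one-sided 2.5%. The 95% row is the same at both levels because the cut-off is the same.

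**Precision example.** For 27 of 30 IPVs occluded, the exact 95% limits are the 2.5% point of Beta(27, 4) and the 97.5% point of Beta(28, 3), giving 73.5 to 97.9%.

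**Several IPVs in one subject.** The plan allows this. Thirty IPVs in 20 subjects average 30/20 = 1.5 each. With design effect 1 + (1.5 − 1) × ICC and an assumed ICC of 0.1 to 0.5, the 30 veins carry the information of 30/1.05 = 28.6 down to 30/1.25 = 24 independent ones. Positive correlation therefore makes the independent-vein figures somewhat optimistic. More than 30 IPVs would generally raise them.

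**The case against.** Three points on the other side have weight.

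First, a reader might infer that items 2 and 3 flatly contradict each other. The text does not go that far. Item 2 is conditional and limited to AEs and MDRs, and it explains why the study is not sized on them. Item 3 opens with technical features and then speaks of performance, which is not defined. If performance means ablation performance only, the two items can stand together. Against that reading, the sentence just before the claim mentions both safety and effectiveness. The fair description is a tension on adverse events if performance includes safety. For occlusion and technical success, the claim is simply unsupported.

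Second, a reader might infer that the study is too small or that the missing calculation is itself a fault. The document discloses that there is no formal calculation, in the same section as the claim, and a small early study may reasonably proceed without one. The size is not the issue. The issue is the capability claimed for it.

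Third, the practical effect is limited. No endpoint, analysis or enrolment number rests on the sentence, and how a regulator would read it is conjecture. The case for equivalence also draws on technical features and existing data. This stands, and it lowers the severity. It does not make the sentence true.

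**Conclusion.** The concern holds as an unsupported statement. Item 3 attributes to the sample a property that the design does not have: there is no comparison arm, named predicate, predicate rate, margin or test. With 30 IPVs and a benchmark fixed in advance, a 20-point shortfall in occlusion would be found more often than not under every benchmark and both test levels tried. A 10-point shortfall would be missed more often than found. For adverse events, the absence of an event type leaves rates up to 11.6% or 16.8% open.

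The zero-event limits need only the sample size and independent subjects. The power figures are illustrations that rest on the assumed benchmarks, test levels and independent veins. The conclusion that *any* difference is too strong does not depend on which of them is chosen.

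Severity is minor to moderate. The documents do not support the inference that the endpoints or the enrolment target are compromised.

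**What to change.** Delete the last sentence of item 3 in section 11.3 and put in its place:

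> The study is not sized to detect differences from the predicate; any comparison is descriptive and will name the device and the source of its rate. Zero events of a given type would exclude true per-subject rates above 16.8% (n = 20) or 11.6% (n = 30) (exact two-sided 95%). As an example, 27 of 30 IPVs occluded gives a 95% CI of 73.5 to 97.9% if veins are independent, and wider if outcomes of IPVs in the same subject are positively correlated.

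In item 4, state that the post-hoc review is descriptive and reported with 95% intervals.

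I would not add to section 11.1 an interval based on an effective sample size estimated from the study data. With 20 to 30 subjects that estimate would be unstable. A fallback to subject-level results when every vein is occluded would make the unit of analysis depend on the outcome.

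The change needs no extra subjects, visits or data, and the sample size stays as it is. The cost is a less favourable statement of what the study can show in the submission, plus the small work of reporting intervals.

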### **2.3.1 Potential Risks**

#### **Risks from undergoing endovenous thermal ablation:**

The Vestico ablation procedure will be performed by trained and registered medical doctors who follow standard of care for RFA. While thermal ablation procedures have inherent risks, problems with the procedure are considered rare, and when they do occur, they are usually minor and easily treated.

Some of the potential risks identified are:

- Edema
- Skin changes
- Venous ulcers
- Deep vein thrombosis
- Superficial vein thrombosis

- Pulmonary embolism
- Venous thromboembolism
- Skin burn
- Thermal injury of adjacent tissues
- Paresthesia
- Infection/cellulitis
- AV Fistula
- Need for re-operation
- Death

Before undergoing ablation procedure, subjects will be informed by the treating clinician of these potential side effects using the clinical informed consent form, in addition to a separate informed consent form for the research study.

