## **CLINICAL PROTOCOL**

A study conducted to evaluate the safety and effectiveness of the Venclose digiRF Generator with Vestico Catheter System (“Vestico”) treating incompetent perforator veins (IPVs). The study will be conducted in compliance with IDE requirements under local IRB approval(s). Study data will be summarized and submitted to FDA in a premarket notification once all subjects have completed 30-day follow-up.

The study working hypothesis is that using the Venclose Vestico Catheter System for treating incompetent perforator veins (IPVs) will not result in any adverse outcomes related to use of the device.

No significant risk is posed by either the use of the Vestico Device or the study process. While safety can never be taken lightly, this study is not meant to measure, monitor or analyze any significant disease or disorder for which medical treatment is mandatory.

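### Section 11.3 item 4 settles substantial equivalence by post-hoc review, with no preset criterion and without technical success; the working hypothesis is worded in two conflicting ways

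*Combined protocol and SAP*

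**What the plan says.** All references are to the combined protocol and SAP.

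**The equivalence conclusion.** Section 11.3 states that the sample size was not formally calculated and plans at least 30 IPVs in 20 to 30 subjects. Item 3 then says: "The proposed sample size for this study is large enough to understand any differences in performance between subject and predicate devices". Item 4 says that a post-hoc review of the results will be "performed on any AEs and/or occlusion data to determine if results provide an acceptable level of substantial equivalence". On use of the data, the Synopsis says: "Study data will be summarized and submitted to FDA in a premarket notification once all subjects have completed 30-day follow-up".

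**The endpoints.** The Clinical Protocol Summary and section 3.1 list two primary endpoints: safety, and technical success (reaching and entering the vein and delivering the planned energy). Occlusion is a secondary endpoint, read by duplex ultrasound at Days 3, 15 and 30.

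**The working hypothesis.** The Synopsis expects treatment "without resulting in any adverse outcomes related to use of the device". The opening statement of the Clinical Protocol says use of the device "will not result in any adverse outcomes related to use of the device". Objective 1 in the Summary, section 2.2 and section 3.1 say instead that it "will not result in significant adverse outcomes related to use of the device".

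**The concern.** Item 4 does more than promise a description of the data. It announces a determination, and the data behind it go to FDA. Nothing in the plan says what result would count as acceptable, at which visit occlusion is judged, or what part the primary effectiveness endpoint plays. The basis for the conclusion can therefore be settled once the results are known, and it need not include technical success.

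The two hypothesis wordings add a second freedom. If a few minor device-related events occur, a report could describe the hypothesis as met or as not met, depending on which page it follows.

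**Working it through.** The plan gives no figure to reproduce: there is no alpha, margin, event rate, performance goal or predicate rate. The check is a comparison of sections, plus the precision that the planned numbers allow.

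**Step 1: look for a criterion elsewhere.**
- Summary and section 3.1, safety: events are monitored and their acceptability is judged after the study. No rate is given.
- Summary and section 3.1, technical success: it is to be evaluated. No threshold is given.
- Section 11.1: methods are left to what is appropriate, with descriptive techniques as possibilities. No interval, test or margin is given.
- Section 3.2, B.v: cessation of flow and of reflux is included in the analysis. No threshold or deciding visit is given.

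None of these supplies what item 4 lacks.

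**Step 2: compare item 4 with the endpoint list.**

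| Endpoint | Status in section 3.1 | Named in item 4? |
|---|---|---|
| Adverse events | Primary (safety) | Yes |
| Technical success | Primary (effectiveness) | No |
| Occlusion, Days 3, 15, 30 | Secondary | Yes, with no visit specified |

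**Step 3: precision for item 3.** Inputs: n = 20 or 30 subjects (section 11.3), all followed to Day 30, at most one count per subject, subjects independent. With zero events the exact (Clopper-Pearson) two-sided 95% upper limit is 1 − 0.025^(1/n).
- n = 20: 1 − 0.025^(1/20) = 16.8%
- n = 30: 1 − 0.025^(1/30) = 11.6%

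With one event the corresponding upper limits are 24.9% (1/20) and 17.2% (1/30).

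For technical success per IPV, taking the minimum of 30 IPVs and treating them as independent, the exact two-sided 95% lower limits are:

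| Successes | Observed | Lower limit |
|---|---|---|
| 30/30 | 100% | 88.4% |
| 29/30 | 96.7% | 82.8% |
| 28/30 | 93.3% | 77.9% |
| 27/30 | 90.0% | 73.5% |

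Several IPVs in one subject would make the real precision worse. With no preset criterion, any of these rows could be called acceptable. With one arm and no predicate rate, none of them can be turned into a difference from the predicate.

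**Step 4: compare the hypothesis wordings.**

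| Place | Device-related outcomes excluded |
|---|---|
| Summary, Synopsis | any |
| Clinical Protocol, opening statement | any |
| Summary, Objective 1 | significant |
| Section 2.2 | significant |
| Section 3.1, Objective 1 | significant |

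The Summary therefore disagrees with itself. Section 2.3 describes a significant-risk device and lists what makes an adverse event serious, but ties neither to the hypothesis, so *significant* has no definition there. Suppose only minor device-related events occur: the first two statements are contradicted and the other three are not.

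**The case against.** The strongest reply is that this is a small, descriptive, investigator-initiated study that openly has no sample size calculation and claims no error control. Its equivalence argument also rests on technical features such as set-point temperature and ablation size (section 11.3, item 3). That stands: the absence of power is not an error here, and no larger sample is asked for. It does not reach item 4, which announces a determination from the study's results.

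Several stronger readings are tempting, and the documents do not support them.

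- *Results might go unreported.* Adverse events, technical success, occlusion and reflux are all to be recorded or evaluated. The gap is which result the conclusion rests on.
- *Either domain alone would suffice.* The and/or in item 4 may only list the data to be reviewed. The text does not settle it.
- *The limits in Step 3 are a floor that no analysis could beat.* They depend on a two-sided level and on counting by subject, and the plan fixes neither. One-sided 95% upper limits for zero events are 13.9% (n = 20) and 9.5% (n = 30), and the number of IPVs has a minimum but no stated maximum.
- *Minor device-related events are what the protocol itself expects.* Section 2.3.1 does say that "problems with the procedure are considered rare, and when they do occur, they are usually minor and easily treated", but about thermal ablation procedures in general; device risks are treated separately. The documents give no device event rate, so no probability can be put on the two wordings diverging.
- *Defining significant by serious outcomes would be empty, because section 2.3 rules those outcomes out.* That statement is conditional on device failure, while death, pulmonary embolism and deep vein thrombosis are on the list of monitored events.
- *Occlusion should be demoted.* It is the effect the device is meant to produce, and item 4 may reasonably use it. The defect is the missing time point and the missing primary endpoint.

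It is also fair to say that the hypothesis mismatch is mainly a matter of reconciling text, since no pass/fail test is attached to either wording.

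**Conclusion.** The concern holds in two limited parts.

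(a) Item 4 plans a conclusion on substantial equivalence with no criterion, no deciding visit for occlusion and no mention of the primary effectiveness endpoint. Item 3's statement about differences from the predicate has no comparator arm or rate behind it. At the planned size, an event-free study would still leave true per-subject rates up to 16.8% or 11.6% inside the two-sided 95% interval, assuming independent subjects with complete follow-up.

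(b) The hypothesis has two incompatible wordings, one of them undefined. This part is a text comparison and rests on no assumed rate.

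Neither part invalidates the study or its descriptive reporting. Both should be corrected before the first treatment, because a criterion chosen later cannot support the determination in item 4.

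**What to change.** 1. **Hypothesis.** Use one wording in the Synopsis, Objective 1 of the Summary, section 2.2, the opening of the Clinical Protocol and section 3.1. If *significant* is kept, define it, for example by cross-reference to the serious-event definition in section 2.3 and the SADE category in the primary safety endpoint. All AEs and ADEs are still reported.
2. **Item 4.** Amend it before the first treatment so that the conclusion rests on safety by subject through Day 30, on technical success, and on occlusion at one time point that the sponsor names in advance, each with an exact 95% interval. Report the vein-level endpoints per IPV and per subject, because the Objectives allow several IPVs in one subject.
3. **The claim.** Unless the sponsor states in advance a criterion and a predicate benchmark attainable with 20 to 30 subjects, report estimates with intervals. In that case remove both the statement that this study determines an acceptable degree of substantial equivalence and item 3's statement on the adequacy of the sample.

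**Cost.** A short text amendment, with no new visits or measurements. Setting a criterion needs a predicate benchmark that the documents do not contain, so the sponsor must supply one or drop the two claims as in point 3. The sponsor gives up choosing the criterion after seeing the data, and without a benchmark makes a more modest claim.
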